7 STUDY VISITS AND PROCEDURES

The study will commence following institutional medical ethics committee and regional competent authority approval. Study evaluation continues until 24 months of follow up post implantation has been obtained on all available participating subjects.

Screening of patients will be performed according to the hospital standard screening for tricuspid valve repair and replacement. In addition, patients will be screened for their suitability for Cardioband therapy. A central eligibility committee will be established to determine final enrolment of patients across all investigational sites. The eligibility committee will include at least a Heart Failure specialist, and an Echocardiography specialist. Patients will give a written consent for health information release prior to screening process. The treatment procedure will be performed according to the instructions outlined in the current approved IFU.

Data will be collected at the following time points (as expected in the course of a surgical treatment): baseline, procedure, discharge and clinical follow-up at 30 days, 6 months, 12 months and 24 months from index procedure. Data from any other additional time points may be collected and analyzed if available.

The procedures associated with each study visit are outlined and summarized in **Table 4**.

TRI-REPAIR – Tricuspid Regurgitation RePAIR with Cardioband Transcatheter System (TR1-1). Study protocol

Procedure	Screening	Baseline	Implantation	Discharge	30 days	6, 12, 24 months
Visit Number	-1	0	1	2	3	4
Range	- 1 month	- 1 month	0	NA	-1 wk/+ 2 wks	+/- 1 month
Data release Consent	X					
Study informed consent		X				
Demographics		X				
Wearable data watch		X	X	X	X	X
Medical History		X				
Routine Blood tests		X		X	X	X
Pregnancy test (if applicable)		X				
General Clinical State		X		X	X	X
Adverse Events		X	X	X	X	X
Medication Profile		X		X	X	X
Tricuspid Regurgitation Assessment by TTE	X	X		X	X	X
Tricuspid Regurgitation Assessment by TEE		X	X			
Tricuspid valve anatomy (by Echo and/or CT)	X					
Coronary Angiography (within the past 12 months, optional)	X					
Cardiac MRI (optional)	X					X
6-minute walk test		X			X	X
QoL questionnaire (KCCQ)		X			X	X
NYHA Functional Class		X			X	X
Cardioband Implantation			X			

Table 4: Schedule of Visits and Procedures

	TRI-REPAIR – Tricuspid Regurgitation RePAIR with CaRdioband Transcatheter System (TR1-1). Study protocol	[REDACTED] [REDACTED] [REDACTED]
---	---	--

7.1 Unscheduled Visits

An unscheduled visit will be any visit to the clinical site other than the specific visits requested in the protocol. The Investigator or trained and qualified investigational staff will perform all procedures necessary to evaluate the study participant at these visits, and record the visit in the subject's chart. At the very least, safety information such as occurrence of adverse events will be recorded during the unscheduled visit. The Principal Investigator must be notified by the subject immediately of any unscheduled visits to any medical facilities during the study period. (Subjects will be instructed to report).

8 CARDIOBAND IMPLANT PROCEDURE

Cardioband is implanted by transfemoral procedure. [REDACTED]
[REDACTED]
[REDACTED]

8.1 Cardioband system procedure

Prior to the procedure, subjects must be evaluated to determine eligibility for transfemoral venous access. Absolute or relative contraindications to transfemoral procedures will be evaluated by the principal investigator and or interventional cardiologist.

The Cardioband system procedure is performed under echocardiography and fluoroscopy guidance. The procedure summarized in the following steps:

1. The subject is prepared as per standard practice for transvenous catheterization.
2. Cardioband implant size is selected according to the tricuspid annulus size measured preoperatively and the implant is mounted as specified in the IFU.
3. The transfemoral steerable sheath (TSS) with the Dilator are inserted through the femoral vein, the tip of the TSS is steered into the RA under echo guidance.
4. After removing the dilator and guidewire, the implant delivery system is inserted.
5. The system is navigated to the anterior part of the annulus, proximal to the aortic root. The first anchor is placed.
6. The system is navigated to the next anchoring site while deploying the implant fabric along the anterior and posterior annulus.
7. Implant deployment and anchoring is continued until the Cardioband implant reaches the coronary sinus opening.
8. The implant is then disconnected from the implant catheter. The Implant Delivery system is removed.
9. The Size adjustment tool (SAT) is then inserted over the implant guidewire and engaged with the implant.
10. Adjustment is performed using the SAT, under echocardiography guidance.
11. After achieving the desired result, the SAT is detached.
12. The System is removed upon completion.

	TRI-REPAIR – Tricuspid Regurgitation RePAIR with CaRdioband Transcatheter System (TR1-1). Study protocol	[REDACTED]
---	---	------------

Additional details on procedures, contraindications, and risks are provided in the device *Instructions for Use*.

9 CLINICAL RISK BENEFIT EVALUATION

9.1 Expected benefits

Tricuspid regurgitation is a significant disease with one year mortality 36.1 %^(3, 4), but less <1% of patients with moderate or severe TR undergo surgery. The vast majority of cases are managed conservatively due to the excessive risk of open heart surgery^(56, 7).

Thus, there is an unmet clinical need for devices enabling to perform a valve repair in a non-invasive fashion and without cardiopulmonary bypass.

Cardioband was proved to lower the surgical risks by using established transfemoral techniques; Based on established annuloplasty surgical devices. Cardioband was showed to reduce the Mitral septo-lateral annular dimension and therefore reduce the MR. MR Reduction accompanied with improvement of the NYHA stage, 6 minute walk test and MLHFQ questionnaire.

Although there are no guaranteed benefits from participation in this study the Cardioband System is expected to allow for treatment of patients that would otherwise not undergo Tricuspid valve repair due to the invasiveness of current techniques. In addition Cardioband enable fine-tuning of the repair by adjusting the device size on a beating heart.

Given these benefits showed for mitral valve repair, there is ample justification for a prospective investigation focusing on the clinical performance and safety of the Cardioband system for treatment of the Tricuspid valve as well.

9.2 Anticipated risks

The potential risks associated with Cardioband can be divided into three categories: First, there are the risks associated with transcatheter repair procedures the patient population (high risk for surgery) and anaesthesia. These risks are expected to be similar to risks that were reported for mitral valve repair by transcatheter devices in similar populations (e.g. Carillion, mitraclip, etc.). Second, there are the risks uniquely associated with annuloplasty procedures using ring/band which similarly are not expected to significantly differ between marketed systems and the Cardioband System. Third, there are risks specifically associated with the Cardioband procedure. The latter are also expected to be similar to those reported for those reported for the use of Cardioband for mitral repair.

A risk analysis according to ISO 14971 Application of Risk Management to Medical Devices has been conducted.

9.3 Potential Risks and Adverse Events

The following ANTICIPATED EVENTS have been identified as possible complications of the Cardioband TF procedure:

1. **Risks associated with the procedure and administration of anaesthesia including but not limited to the following:** Death; Stroke/ transient ischemic attack; Haemolysis; Heart block; Perforation or damage of vessels, myocardium or valvular structures; Pericardial

	TRI-REPAIR – Tricuspid Regurgitation RePAIR with CaRdioband Transcatheter System (TR1-1). Study protocol	  
---	---	---

effusion/cardiac tamponade; Haematoma; Blood loss requiring transfusion; Infection including endocarditis and septicaemia; Arrhythmia; Air embolus; Thromboembolism; Fever; Hypertension/hypotension; Allergic dye reaction; Allergic Anaesthesia reactions; Aneurysm; Atrial Septal defect requiring intervention; Arterio-venous fistula; Cardiac Arrest; Coagulopathy; Deep Venous thrombus (DVT); Dyspnoea; Edema; Esophagus irritation; Esophagus perforation or stricture; Gastrointestinal bleeding or infarct; Hematoma; Haemolysis; Haemorrhage requiring transfusion; Infection and pain in insertion or incision site; Lymphatic complication; Mesenteric ischemia; Multi-system failure; Myocardial infarction; Nausea/vomiting; Peripheral ischemia; Prolonged angina; Prolonged ventilation; Pulmonary Congestion; Pulmonary thrombo-embolism; Renal insufficiency; Respiratory failure/atelectasis/pneumonia; septicaemia; Urinary tract infection; Vascular trauma, dissection or occlusion; Vessel spasm; vessel perforation or laceration; worsening heart failure .

2. **Potential risks specifically associated with the use of annuloplasty rings/bands include, but may not be limited to the following:** reoperation and explants; residual or recurrent or worsening regurgitation requiring intervention; haemolysis; conduction system disturbances including atrioventricular block; endocarditis; low cardiac output; right heart failure; failure or degeneration of the natural valvular apparatus due to progression of disease; inadequate repair of the valvular and subvalvular structure; detachment/dislodgment (partial or full) of the annuloplasty ring/band from its site of attachment; migration or malposition; malfunction of the ring/band due to distortion or fracture at the implant or physical or chemical deterioration of band components; bleeding complications related to use of anticoagulant therapy; prosthesis thrombosis; infection.
3. **Risks specifically associated with the Cardioband, in addition to the general risks of annuloplasty, include, but may not be limited to the following :**Conversion to standard valve surgery; Failure to deliver the band to the intended site; tissue damage or vascular injury due to anchor insertion; Unsuccessful adjustment of the band; Tissue damage from insertion and removal of system components; Cardioband components embolism; Partial device dehiscence (anchor detachment) and disturbances to the conduction system.

The potential for the occurrence of device dehiscence, device mal-position, and residual or recurrent regurgitation requiring intervention is expected to be similar to that seen for Mitral valve repair with the Cardioband device. Clinical study for MR repair have demonstrated that Cardioband procedure is relatively safe and can reliably result in a significant reduction of the annular septo-lateral dimension and MR, and functional improvement in patients with FMR ⁴⁶⁾.

As with any device undergoing clinical investigation, there may be unforeseeable risks, which are not known at this time. Medical and/or surgical intervention may be required to correct clinical complications associated with the device procedure.

	TRI-REPAIR – Tricuspid Regurgitation RePAIR with CaRdioband Transcatheter System (TR1-1). Study protocol	[REDACTED] [REDACTED] [REDACTED]
---	---	--

9.4 Risk/benefit ratio

Cardioband proposes a less invasive, fully adjustable, direct annuloplasty for tricuspid regurgitation repair, and as presented above targets an unmet clinical need for Tricuspid repair in a patients that are at high risk for surgery.

Cardioband had shown to enable a “surgical annuloplasty” for mitral regurgitation repair through a percutaneous approach. [REDACTED]

[REDACTED]

[REDACTED] The benefit–risk profile is expected to be similar for the tricuspid regurgitation annuloplasty repair and will be rigorously addressed in the clinical trial.

10 ADVERSE EVENTS AND ADVERSE DEVICE EFFECTS

10.1 Reporting requirements

Timely and complete reporting of Adverse Events (AE) and safety assessments allows:

- Protection of safety and study subjects.
- Greater understanding of the overall safety profile of the study treatment.
- Appropriate modification of study protocols and improvement in study design and procedures.
- Adherence to regulatory requirements.

The definitions and reporting requirements adopted in this study are derived from the current International standard on clinical investigations: EN ISO 14155:2011 Clinical Investigations of medical devices for human subjects – Good Clinical Practices.

10.2 Definitions

Based on ISO 14155:2011

Adverse event

Any untoward medical occurrence, unintended disease or injury or any untoward clinical signs (including an abnormal laboratory finding) in subjects, users or other persons whether or not related to the investigational medical device. This includes events related to the procedures involved.

This definition does not imply that there is a relationship between the adverse event and the device under investigation. An AE can therefore be any unfavorable and unintended sign, symptom,

	TRI-REPAIR – Tricuspid Regurgitation RePAIR with CaRdioband Transcatheter System (TR1-1). Study protocol	[REDACTED] [REDACTED] [REDACTED]
---	---	--

laboratory observations or disease temporally associated with the use of the investigational product, whether or not related to the investigational product.

The following should be reported as AE:

- Untoward medical conditions or signs or symptoms that were absent before starting study treatment.
- Untoward medical conditions or signs or symptoms present before starting study treatment and worsen (increase severity or frequency) after starting study treatment.
- Abnormal laboratory values or tests which are clinically significant.
- Clinical signs or symptoms that require therapy.

Adverse device effect (ADE)

Adverse event related to the use of an investigational medical device. This includes any adverse event resulting from insufficiencies or inadequacies in the instructions for use, the deployment, the implantation, the installation, the operation, or any malfunction of the investigational medical device. This includes any event that is a result of a use error or intentional misuse.

Therefore, some adverse device effects may be related to device deficiencies, defined as follows:

Device deficiency

Inadequacy of a medical device related to its identity, quality, durability, reliability, safety or performance. Device deficiencies include malfunctions, misuse or use errors and inadequate labeling.

- **Device Malfunction**: failure of an investigational medical device to perform in accordance with its intended purpose when used in accordance with the instructions for use or clinical investigation protocol.
- **Use Error**: act or omission of an act by the user that results in a different medical device response than intended by the manufacturer or expected by the user. Use error includes slips, lapses, and mistakes. An unexpected physiological response of the patient is not by itself considered use error.

A device deficiency shall be reported as AE or SAE according to the AE and SAE definitions.

Device deficiencies that did not lead to an adverse event but could have led to a medical occurrence if:

- A suitable action had not been taken,
- intervention had not been made
- circumstances had been less fortunate,
- Shall be reported as well as an adverse event.

Serious adverse event (SAE)

Adverse event that

- a) Led to a death,
- b) Led to a serious deterioration in the health of the subject that either

	TRI-REPAIR – Tricuspid Regurgitation RePAIR with CaRdioband Transcatheter System (TR1-1). Study protocol	
---	---	---

- 1) Resulted in a life-threatening illness or injury, or
 - 2) Resulted in a permanent impairment of a body structure or a body function, or
 - 3) Required in-patient hospitalization or prolongation of existing hospitalization, or
 - 4) Resulted in medical or surgical intervention to prevent life threatening illness or injury or permanent impairment to a body structure or a body function.
- c) Led to foetal distress, foetal death or a congenital abnormality or birth defect

NOTE: A planned hospitalization for pre-existing condition, or a procedure required by the CIP, without a serious deterioration in health, is not considered to be a serious adverse event.

Unanticipated serious adverse device effect (USADE)

Serious adverse device effect which by its nature, incidence, severity or outcome has not been identified in the current version of the risk analysis report.

NOTE: Anticipated serious adverse device effect (ASADE) is an effect which by its nature, incidence, severity or outcome has been identified in the risk analysis report.

10.3 Reporting procedures

Adverse event and adverse device effect information will be collected throughout the study. The investigator or research coordinator will record these events on the CRF's. The event, date of onset, severity, duration, and relationship to the device will be recorded. Any adverse event will be monitored until it is adequately resolved or stabilized.

The investigator has the responsibility to report adverse events as they occur:

- The Ethics Committee must be informed of any serious adverse device effect.
- Valtech and the monitor must be informed of any adverse event without undue delay.
- All serious adverse events must be reported by completing a serious adverse event eCRF form as soon as of knowledge of the event. An automatic notification will be generated to Valtech and to the monitor upon the issue of such eCRF. Investigator should not wait to receive additional information to fully document the SAE, and should start the completion of the electronic form as soon as possible. The report of SAE should be followed by a full written report detailing relevant aspects of the SAE in question. Where applicable, information from relevant medical records and autopsy reports should be obtained.
- Other adverse events must be reported as soon as possible.

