5.5.3 Analysis of performance and safety endpoints

The performance and safety endpoints of the Cardioband System will be assessed by recording the echocardiographic parameters and by monitoring the patient clinical status. Safety assessments will consist of recording of all adverse events, and regular monitoring of haematology and blood chemistry parameters, and vital signs. These parameters are evaluated during the patients' follow-up visits.

Study results will be presented in tabular format. Two sided 95% exact confidence intervals will be presented where required. Continuous variables will be summarized by a mean, standard

	TRI-REPAIR – Tricuspid Regurgitation RePAIR with Cardioband Transcatheter System (TR1-1). Study protocol	
---	---	---

deviation, minimum, median and maximum. Categorical variables will be summarized by a count and percentage. If statistical tests will be done the significance level will be equal to or lower than 5%. Nominal p-values will be presented. Where confidence limits are appropriate, the confidence level will be 95%.

Baseline demographic and other baseline characteristics, together with safety analyses will be performed on all subjects.

The numbers of subjects who entered and completed each visit of the study will be provided, as well as the reasons for all discontinuations, grouped by major reason (e.g., lost to follow-up, adverse event, etc.). A list of discontinued subjects, protocol deviations, and subjects excluded from the efficacy analysis will be provided.

Descriptive statistics will be provided for the efficacy and safety outcome results.

The analysis of all adverse events will include incidence tables and incidence tables by severity, relationship to treatment and baseline parameters. Serious adverse events will be listed and discussed individually.

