10.3.1 Adverse Events Reporting Requirements in Germany

In Germany, events will be reported in accordance with the "Medizinprodukte-Sicherheitsplanverordnung" (MPSV).

According to MPSV § 3 Nr.5 and 6, serious adverse events occurring during clinical investigations must be notified by the Sponsor and Investigator.

The investigator will report to the sponsor within 24 hours of having information of an event occurred.

	TRI-REPAIR – Tricuspid Regurgitation RePAIR with CaRdioband Transcatheter System (TR1-1). Study protocol	[REDACTED] [REDACTED] [REDACTED]
---	---	--

The sponsor's reporting to BfArM (Bundesinstitut für Arzneimittel und Medizinprodukte, the Federal Institute for Drugs and Medical Devices) as per regulation, will be performed immediately of the sponsor becoming knowledge of the occurrence of the SAE.

1. For SAEs occurring in Germany, where a causal relationship between the SAE and the investigational medical device, the study or the study procedure cannot be excluded reporting will be made using the current SAE Report Form provided by BfArM.
2. For SAEs occurring in other countries, where the clinical trial is performed and where a causal relationship between the SAE and the investigational medical device, the study or the study procedure cannot be excluded reporting will be made using the MEDDEV Form / Summary table.
3. For all SAEs occurred where a causal relationship between the SAE and the investigational medical device can be excluded reporting to BfArM will be made on a quarterly basis by sending the MEDDEV Form.

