10.5 Monitoring of adverse event documentation

During the monitoring visit, the monitor must perform the following verification activities:

- Confirmation of the accuracy of subject information supplied by the investigator concerning the seriousness of the event and causal relationship to the device;
- Ensuring that the appropriate adverse event CRFs have been completed by the site personnel;
- Verification of whether or not the investigator has followed established reporting procedures and, if required, has reported the event to Valtech and/or the EC, as appropriate.
- Confirmation that copies of EC reports and correspondence are maintained in the Site Regulatory Binder.

[figure not shown]

For any negative change in subject test results, clinical status, or treatment (e.g., increased dose of diuretic, reduction in ejection fraction), the monitor must ensure that the corresponding AE has been documented. If a reportable AE is discovered that has not been reported, the Monitor must immediately initiate the proper reporting procedures in collaboration with the investigator, as defined by applicable regulatory requirements. If the change is not associated with an AE, the reason for the change must be appropriately explained on the appropriate CRF or narrative form.

Any problems identified during these activities should be documented in writing and notified to Valtech.

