10.7 Clinical Events Committee

All Serious adverse events will be reviewed by an independent Clinical event Committee (CEC) for adjudication of the event relation to the study device or procedure. Major SAEs and SAEs that are related or possibly related to device or procedure will be reviewed by all CEC members, other SAEs will be reviewed by the CEC chairperson.

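### Relation to the procedure is not captured for non-serious adverse events, so the planned table by relationship to treatment lacks a source for harms due only to TEE, anaesthesia or contrast

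*Protocol*

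**What the plan says.** Protocol 10.3 sets out the items recorded for every adverse event: "The event, date of onset, severity, duration, and relationship to the device will be recorded". Protocol 10.5 gives the monitor the matching check: "Confirmation of the accuracy of subject information supplied by the investigator concerning the seriousness of the event and causal relationship to the device". Neither section mentions relation to the procedure.

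Procedure relation does appear elsewhere, but only for serious events. Under 10.7 the Clinical Events Committee (CEC) reviews all serious adverse events "for adjudication of the event relation to the study device or procedure". In 10.3.1, the rule for reporting to the German authority applies "where a causal relationship between the SAE and the investigational medical device, the study or the study procedure cannot be excluded reporting will be made".

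The planned output is wider than either of these. For all adverse events, Protocol 5.5.3 promises "incidence tables by severity, relationship to treatment and baseline parameters". The word treatment is not defined there as device, procedure or both. SAP 4.5.1 and 4.5.2 list site-reported adverse events and CEC-adjudicated serious events as table topics, with no breakdown by relationship and no derivation rule.

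The protocol also treats procedural harm as a category in its own right. The adverse event definition in 10.2 adds: "This includes events related to the procedures involved". Section 9.3 opens its list of anticipated events with a separate class, "Risks associated with the procedure and administration of anaesthesia including but not limited to the following", placed ahead of the classes for annuloplasty bands and for Cardioband itself.

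**The concern.** The treatment is an implant delivered by catheter, under echocardiographic and fluoroscopic guidance, with anaesthesia among its stated risks. Some of its harms come from the band and its delivery system, and others from what surrounds the implantation. The first class in 9.3 includes oesophageal irritation, nausea and vomiting, and allergic reactions to dye or anaesthetic. Events of this kind are often non-serious and need not arise from use of the device.

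A site that follows 10.3 literally has one causality question to answer for such an event, and it is about the device. The CEC does not see non-serious events, so no later step in the plan adds the missing judgment. The study is single-arm, so there is no control group to show the background rate of these events, and the report will lean on attribution. At stake is whether the relationship table gives a full count of treatment-related morbidity, and whether it can separate harm from the band from harm of the procedure, as the protocol's own risk section does.

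**Working it through.** The documents state no figure on this point, so there is nothing to reproduce. The check is a comparison of what is collected with what is to be tabulated.

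1. Site recording, all adverse events (Protocol 10.3): device relation only.
2. Monitor verification (Protocol 10.5): seriousness and device relation only.
3. CEC adjudication (Protocol 10.7): device or procedure, serious events only.
4. Authority reporting (Protocol 10.3.1): device, study or study procedure, serious events only.
5. Planned table (Protocol 5.5.3): all adverse events by relationship to treatment, source variable not named.
6. SAP 4.5.1 and 4.5.2: no relationship rule.

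For serious events, items 3 and 4 supply a procedure judgment. For non-serious events, items 1 and 2 are all there is. The table in item 5 covers both groups, so for the non-serious group its only specified source is device relation.

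The next question is which non-serious events this leaves out. Under 10.2 an adverse device effect is any event related to use of the device, including its deployment, implantation and operation. Protocol 4.2.2 counts the transfemoral steerable sheath and its dilator as parts of the Cardioband system. A groin or vein injury caused by the sheath can therefore properly be recorded as device-related. What remains is harm due only to TEE, anaesthesia or contrast.

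The size can be written only in symbols. Let d be the number of subjects with at least one device-related event, and p the number whose only related events are non-serious and due solely to TEE, anaesthesia or contrast. Take the planned maximum of 60 subjects as denominator.

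- Rate with both relations captured: (d + p)/60.
- Rate shown if every such event is counted as unrelated: d/60.
- Rate shown if sites treat every such event as related: (d + p)/60.
- Possible shortfall: from 0 to p/60, that is 1/60 = 1.7 percentage points per subject.

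The documents give neither d nor p, so no numerical estimate follows.

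**The case against.** The strongest reply is that the consequence is small. The primary safety endpoint and the stopping rule rest on serious events, all of which reach the CEC. A TEE or anaesthesia injury that prolongs the hospital stay meets the definition of a serious event and is reviewed there too. No event is lost: every adverse event is recorded, and overall incidence is tabulated whatever its attribution. The SAP has no pre-specified hypotheses, so no test depends on this column. All of this stands, and it limits the point to one descriptive breakdown.

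A second reply is that defining relationship to treatment in the SAP would be enough. That would remove the ambiguity in the table. It would not supply a procedure judgment for non-serious events, and analysts cannot reliably reconstruct one afterwards.

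Three stronger readings are tempting, and the documents do not support them.

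- A reader might infer that these events will certainly be tabulated as unrelated. Treatment is undefined, 10.3 does not say its list is exhaustive, and the eCRF, which may hold a procedure field, is not among the documents.
- A reader might include access-site harms. The sheath and dilator belong to the investigational system, so these can already count as device-related.
- A reader might infer that the CEC has no site information on procedure relation for serious events. Section 10.3 requires a serious event form followed by a full written report, 10.3.1 makes procedure relation part of the reporting test, and the CEC adjudicates it for every serious event. The routing in 10.7 decides only whether all members or the chairperson alone review the event.

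**Conclusion.** The gap is real and narrow. As written, the plan specifies no source for the procedure relation of non-serious adverse events, yet it promises a table of all adverse events by relationship to treatment. Harms due only to TEE, anaesthesia or contrast may be counted as unrelated or classified inconsistently between sites. Where they are counted as unrelated, the treatment-related rate is too low.

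The amount cannot be derived from the documents. The conclusion assumes that the eCRF follows the list in 10.3. If it already has a procedure field, only the wording of 10.3, 10.5 and the SAP needs to catch up. The primary endpoint of major serious adverse events and the stopping rule are not affected. This is a cheap improvement to the safety reporting and does not threaten the study's main conclusions.

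**What to change.** In Protocol 10.3, record two causality fields for every adverse event: relation to the device, and relation to the index procedure, including imaging and anaesthesia. In 10.5, have the monitor verify both. State that an event may be related to both, so that sheath and dilator injuries stay within device relation as 4.2.2 and 10.2 allow.

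In SAP 4.5.1 and 4.5.2, tabulate device-related, procedure-related and either, and name either as the source for the relationship-to-treatment table in Protocol 5.5.3. For 4.5.2 the CEC already adjudicates both relations, so only the layout changes.

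The cost is one more eCRF field, one query round for events already entered, and extra table columns. The reported treatment-related rate may become less favourable. No endpoint, visit or sample size changes. The field should be added while sites can still judge the events, because causality for non-serious events is hard to recover later.
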